7.1.2. Criteria for Temporary Interruption (Withholding) of Study Drug

7.1.2.1. Infection-Related Criteria for Temporary Withholding of Study Drug

Temporary withholding of study drug is required for the development of any of the following infection-related criteria during the study:

- Serious or opportunistic infections, as defined in Exclusion Criteria (Section 5.2). Study drug is to be withheld until resolution of all acute clinical signs and symptoms, and completion of all appropriate anti-infective treatment (exception for LTBI, noted below).
- Participants diagnosed with LTBI during the study are to be permanently discontinued from study drug unless the participant is a candidate for LTBI treatment, and is treated for LTBI as follows:
 - Study drug is temporarily withheld for at least the first 4 weeks of LTBI treatment.
 - After receiving at least 4 weeks of appropriate LTBI therapy (as per World Health Organization and/or the United States Centers for Disease Control guidelines), if there is no evidence of hepatotoxicity (ALT/AST must remain ≤ 2 times ULN) or other treatment intolerance, study drug may be resumed.
 - The participant must complete appropriate LTBI therapy to remain eligible to receive study drug.
- HBV DNA results that are reported as positive, or as detecting HBV DNA, but HBV DNA is below the level of quantification. The sponsor's designated medical monitor should be contacted regarding study status of the participant. HBV DNA testing is to be repeated as soon as is feasible. If HBV DNA is confirmed as positive, the participant must be permanently discontinued from study drug (Section 7.1).

7.1.2.2. Other Criteria for Temporary Withholding of Study Drug

In some circumstances, it may be advisable to temporarily interrupt study drug as a result of adverse events or abnormal laboratory values that have an unclear relationship to study drug. Except in an emergency, the investigator should consult with sponsor's designated medical monitor whenever possible before temporarily withholding study drug for reasons not specified in Section 7.1.2.1 above.

7.2. Participant Discontinuation/Withdrawal from the Study

Participant discontinuation (withdrawal from the study) is expected to be uncommon.

A participant will withdraw from the study in the following circumstances:

- at any time at his or her own request, or at the request of his or her designee (for example, parents or legal guardian)
- at the discretion of the investigator for safety, behavioral, compliance, or administrative reasons

- if the participant enrolls in any other clinical study involving an investigational medicinal product or enrollment in any other type of medical research judged not to be scientifically or medically compatible with this study
- if the participant, for any reason, requires treatment with another therapeutic agent that has been demonstrated to be effective for treatment of the study indication. In this case, discontinuation from the study occurs prior to introduction of the new agent.

Data collection and follow-up for participants who discontinue the study

At the time of discontinuing from the study, an ETV should be conducted, if possible, as shown in the SoA (Section 1.3). See the SoA for data to be collected at the time of study discontinuation and follow-up and for any further evaluations that need to be completed. The participant will be permanently discontinued both from the study drug and from the study.

No follow-up procedures will be performed for a participant who withdraws informed consent unless he or she has explicitly provided permission and consent.

Withdrawal of consent for disclosure

If the participant withdraws consent for disclosure of future information, the sponsor may retain and continue to use any data collected before such a withdrawal of consent. If a participant withdraws from the study, he or she may request destruction of any samples taken and not tested, and the investigator must document this in the site study records.

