6.5. Concomitant Therapy

Participants will be instructed to consult the investigator or other appropriate study site personnel before taking any new medications or supplements during the study. The sponsor's medical monitor should be contacted if there are any questions.

Recording of concomitant therapy

Any medication or vaccine (including over-the-counter or prescription medicines, vitamins, and/or herbal supplements) that the participant is receiving at the time of enrollment or receives during the study must be recorded along with

- reason for use,
- route of administration, and
- dates of administration, including start and end dates.

For concomitant therapies of special interest, dosage information will also be collected as well as reason for use and route and dates of administration.

Allowed concomitant therapy

Participants will maintain their usual medication regimen for SLE and for any other diseases throughout the study unless specifically excluded in the protocol (Section 5.2). Doses must be stable prior to randomization, as stated in the exclusion criteria. Permitted concomitant background standard-of-care medications for SLE can include any combination of these:

- NSAIDs,
- a single antimalarial (such as hydroxychloroquine, chloroquine, or quinacrine),
- a single oral immunosuppressant from the following list: methotrexate, azathioprine, mycophenolate mofetil, or mizoribine,
- a single corticosteroid.

Dose adjustment for NSAIDs, antimalarials, and immunosuppressants

Doses of NSAIDs intended for treatment of signs and symptoms of SLE, antimalarials, and immunosuppressants should not be adjusted during the study's double-blind treatment period. Participants who require initiation or increase in dosage of NSAIDs for treatment of signs and symptoms of SLE, or of antimalarials, or of immunosuppressants after randomization may remain in the study and continue receiving study drug.

Dose adjustment for corticosteroids

See Section 6.5.1.

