6.5.1. Corticosteroid Management Program

Key elements of the corticosteroid management program of this study include the following:

- Participants are restricted to prednisone ≤ 20 mg per day (or equivalent) at randomization (Visit 2), having been on stable doses for at least 2 weeks prior to randomization.
- Following randomization, the dose of prednisone (or equivalent) should not be increased above the participant's background level.
- Participants on >10 mg per day are required to taper their dose to ≤ 10 mg per day by Week 12 to be considered **responders**.
- The corticosteroid doses should not be changed after Week 18.
- Participants with intolerable or exacerbating disease are allowed access to standard-of-care therapy, including increasing the dose of prednisone (or equivalent). Such participants are allowed to remain in the study and continue receiving study drug, but they will be considered **nonresponders** for the efficacy analyses from the time of the medication change onward.

Guidance on corticosteroid tapering

The following guidance on corticosteroid tapering is provided for participants taking >10 mg prednisone (or equivalent) at baseline.

- Steroid tapering should begin no sooner than 4 weeks after randomization.
- Tapering should include a stepwise reduction in 2.5 mg/d to 5 mg/d increments, with each step reduction occurring at 2-week intervals. Thus, the stepwise reduction will occur in intervals that are consistent with the visit schedule.
- Participants who do not tolerate a reduction can increase the dose up to, but not exceeding, the dose at randomization.

Under this schedule, a participant on the highest allowed dose of 20 mg per day at randomization would taper his or her steroid dose in 2.5 mg per day increments at 2-week intervals to achieve the target of ≤ 10 mg per day in time for the assessments at Week 12.

Participants who are taking ≤ 10 mg prednisone (or equivalent) at baseline may have their dose tapered at the discretion of the investigator. However, the corticosteroid doses should not be changed after Week 18.

These recommendations recognize that there is variability in how corticosteroids are administered. The intent is to allow investigators flexibility in how corticosteroids are tapered for individual participants, provided that the participants reach the goal of ≤ 10 mg per day in time for the assessments at Week 12.

Concomitant therapy after permanent discontinuation of study drug

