6.5.3. Supportive Estimand for Primary and Secondary Objectives

A supportive estimand for the primary and secondary objectives will be considered to address a clinical question: What is the difference between LY3471851 and placebo in the target patient population, in achieving successful response at Week 24 without regards to violation of concomitant medication rules?

For the supportive estimands, a **treatment policy estimand strategy** will be used to account for ICEs, and treatment effect will be assessed regardless of whether ICEs has occurred or not. That is, observed data after ICEs will be included as is in the analysis. Population, endpoints, and population-level summary are the same as described in Sections 6.5.1 and 6.5.2.

The image shows the letters 'CCI' in a large, bold, red serif font. The letters are set against a solid black rectangular background. The 'C' and 'I' have a classic, slightly ornate design, while the 'C' in the middle is a simple, clean serif. The overall appearance is that of a corporate or institutional logo.

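### Protocol 7.2 requires withdrawal before a new effective SLE agent is started, while 6.5 and 6.5.1 let participants who start background SLE agents stay on study drug

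*Protocol*

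**What the plan says.** Protocol 7.2 lists the circumstances in which a participant will withdraw from the study. One is that the participant, whatever the reason, "requires treatment with another therapeutic agent that has been demonstrated to be effective for treatment of the study indication". In that case "discontinuation from the study occurs prior to introduction of the new agent". The consequence is complete: "The participant will be permanently discontinued both from the study drug and from the study".

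Protocol 6.5 covers changes to background drugs after randomization. It begins "Participants who require initiation or increase in dosage of NSAIDs for treatment of signs and symptoms of SLE", goes on to antimalarials, and ends "or of immunosuppressants after randomization may remain in the study and continue receiving study drug". Protocol 6.5.1 gives participants whose disease is intolerable or worsening access to standard-of-care therapy, with a higher prednisone dose as one example, and adds: "Such participants are allowed to remain in the study and continue receiving study drug". They count as nonresponders from the change onward.

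Protocol 2.2 describes SLE standard of care as corticosteroids, NSAIDs, antimalarials, cytotoxic agents and immunosuppressants. Section 7.2 does not refer to 6.5 or 6.5.1, and the protocol does not define which agents count as demonstrated to be effective.

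On the analysis side, SAP 6.5.3 sets a supportive treatment policy estimand under which "observed data after ICEs will be included as is in the analysis". SAP Appendix 2 analyses it for SLEDAI-4 by logistic regression with nonresponder imputation (NRI) and labels it exploratory. Protocol 9.4.6.2 also commits to a treatment policy analysis.

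**The concern.** A participant who starts, say, an immunosuppressant for the first time at Week 10 fits both rules. Under 6.5 the participant may stay on study drug and be assessed through Week 24. Under 7.2, if the agent counts as effective in SLE, the participant must have left before the first dose of it. One section allows what another forbids, and a site following either can point to protocol text.

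At stake is whether data after the start of a new agent are collected in the same way everywhere. The treatment policy question asks what happens regardless of such starts, so it depends on those data. If some sites keep starters and others withdraw them, the result partly reflects which section a site applied. Time on study drug and the counts of participants who discontinue treatment or study depend on the same choice.

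**Working it through.** **The plan's own figure.** Protocol 9.2 and SAP 6.1 give 70 per group, response 0.40 against 0.64, two-sided alpha 0.05 and at least 80% power. With the pooled-variance normal approximation, the mean rate is 0.52 and

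z = [0.24 × √70 − 1.96 × √(2 × 0.52 × 0.48)] / √(0.40 × 0.60 + 0.64 × 0.36) = (2.008 − 1.385) / 0.686 = 0.91,

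so power is 81.8%. The statement reproduces, and the conflict does not touch it. The point itself rests on wording.

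**The rules side by side.**

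| Event after randomization | Protocol 6.5 / 6.5.1 | Protocol 7.2 |
|---|---|---|
| Starts an antimalarial or immunosuppressant not taken before | May stay, on study drug | Leaves first, if the agent counts as effective in SLE |
| Starts an NSAID for SLE | May stay, on study drug | Same condition |
| Starts a corticosteroid or other standard-of-care therapy for worsening disease | May stay, on study drug; nonresponder from then on | Same condition |
| Raises the dose of a background drug already taken | May stay, on study drug | Not clearly reached: the text speaks of *another* and a *new* agent |

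The first three rows conflict. The fourth does not.

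**Tracing a new start through the analyses.**

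1. *Primary SLEDAI-4 at Week 24.* For corticosteroids, antimalarials and immunosuppressants, a kept starter is a nonresponder through the medication rule (SAP 6.5.1 and 6.14), and a withdrawn starter through discontinuation and NRI (Protocol 9.4.1 and 9.4.2, SAP 6.11). The result is the same.
2. *NSAIDs.* SAP 6.5.1, 6.14 and 6.15 leave NSAIDs off the violation list; SAP 6.9 includes them. Under the shorter list a kept NSAID starter could be a primary responder and a withdrawn one could not. This matters only if a site treats an NSAID as a 7.2 agent.
3. *Treatment policy analysis.* A kept starter contributes the observed Week 24 result. A withdrawn starter has an early termination visit before the new agent, and the follow-up schedule as published lists no SLEDAI-2K. Week 24 is missing, and NRI makes it nonresponse.
4. *Exposure and disposition* (SAP 6.19.1 and 6.8). The withdrawn starter has shorter exposure and counts as discontinued.

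**Size, on assumed inputs.** The documents give no initiation rate.

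- Affected participants per arm: 70 × 0.05 = 3.5, about 4; 70 × 0.20 = 14.
- Let f be the share of an arm that starts a new agent and r the share of starters who would respond at Week 24 if kept. Withdrawing all starters instead of keeping all of them lowers that arm's treatment policy response rate by f × r. Take r as 0.30–0.50.
- Placebo, f = 0.05–0.20: from 0.05 × 0.30 = 1.5 points to 0.20 × 0.50 = 10 points.
- Active, f = 0.05–0.10: from 1.5 points to 0.10 × 0.50 = 5 points.
- With the same r in both arms, the treatment difference changes by (f placebo − f active) × r. For the pairs 0.05/0.05, 0.10/0.05, 0.15/0.05 and 0.20/0.10 this is 0 to 5 points. With the f ranges fully crossed it runs from (0.05 − 0.10) × 0.50 = −2.5 to (0.20 − 0.05) × 0.50 = +7.5 points.

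A positive change favours active and arises when more placebo participants start an agent. These are all-or-nothing contrasts; a mixture of site practices falls between them and zero if both arms have the same mix.

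**The case against.** The best reply is that the specific governs the general. Sections 6.5 and 6.5.1 name drug classes and say what happens; 7.2 names none. On that reading 7.2 covers agents outside the permitted background list, such as the biologics, JAK inhibitors, calcineurin inhibitors and cyclophosphamide in the exclusion criteria. Other text fits: Protocol 9.4.1.3 plans to analyse starters as nonresponders from the day of the change, 7.2 expects withdrawals to be uncommon, and 6.5 sends questions to the medical monitor. Standard of care is also not the 7.2 trigger; the trigger is demonstrated effectiveness, and Protocol 4.2 says there are few approved SLE therapies.

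This may well be the intent, but no sentence says so. The 7.2 trigger is undefined, it applies whatever the reason, and 6.5.1 gives a prednisone increase only as an example, so neither side marks the boundary.

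The reply does succeed against three stronger readings that a reader might infer.

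- *Dose increases also trigger 7.2.* Raising a background drug introduces no new agent, so counting everyone who starts or increases a drug would overstate the number affected.
- *The treatment policy analysis becomes a copy of the primary one.* Participants who raise a dose, or take prednisone above 10 mg/day after Week 12, need no new agent. They can stay and supply observed data.
- *Safety follow-up is lost.* Protocol 4.1 gives withdrawn participants an early termination visit and post-treatment visits. Unless consent is withdrawn, what changes is mainly time on study drug.

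**Conclusion.** The contradiction is real and narrow. For a participant who newly starts an agent in a class named in 6.5, or standard-of-care therapy under 6.5.1, the protocol allows continuation in one place and requires prior withdrawal in another, for any agent regarded as effective in SLE. The primary conclusion and the power statement do not move for corticosteroids, antimalarials and immunosuppressants; NSAIDs are a conditional exception because the SAP's lists differ.

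The effect falls on an exploratory analysis and on exposure and disposition. If 5–20% start a new agent, about 4–14 of 70 participants per arm are affected. On the response assumptions above, the treatment policy difference could change by 0 to 5 points, or −2.5 to +7.5 with the rates crossed, against a design difference of 24 points. All these rates are assumptions. The NRI consequence follows SAP Appendix 2; under the logistic random effects model named in Protocol 9.4.6.2 the withdrawn participant's later visits would be missing rather than set to nonresponse, but would still be absent. The point should be corrected because the plan commits to the analysis and the correction is cheap.

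**What to change.** Reconcile Protocol 6.5, 6.5.1 and 7.2 so that all three state the same agents that lead to withdrawal and the same agents that do not, with cross-references. Say explicitly how a first start of a permitted class is treated, as distinct from a dose increase. Which agents belong on which list is for the sponsor; this review takes no position. The aim is that data after a new start are collected in one way at all sites.

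The cost is a protocol clarification and a site notice. No change to sample size or the primary analysis is needed. When the wording is settled, the SAP's lists of medication violations should also agree on NSAIDs, which closes the one route by which the choice could reach the primary endpoint.

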7.2.1. Discontinuation of Inadvertently Enrolled Participants

If the sponsor or investigator identifies a participant who did not meet enrollment criteria and was inadvertently enrolled, then the participant should be discontinued from study treatment unless there are extenuating circumstances that make it medically necessary for the participant to continue on study treatment. If the investigator and the sponsor's clinical research physician agree that it is medically appropriate to continue, the investigator must obtain documented approval from the sponsor's clinical research physician to allow the inadvertently enrolled participant to continue in the study with or without treatment with investigational medicinal product. Safety follow-up is as outlined in the SoA (Section 1.3), Section 8.2 ("Safety Assessments), and Section 8.3 ("Adverse Events and Serious Adverse Events") of the protocol.

7.3. Lost to Follow up

A participant will be considered lost to follow-up if he or she repeatedly fails to return for scheduled visits and is unable to be contacted by the study site. Site personnel are expected to make diligent attempts to contact participants who fail to return for a scheduled visit or were otherwise unable to be followed up by the site.

8. Study Assessments and Procedures

Study procedures and their timing are summarized in the SoA (Section 1.3). Protocol waivers or exemptions are not allowed.

Adherence to the study design requirements, including those specified in the SoA, is essential and required for study conduct.

8.1. Efficacy Assessments

Efficacy and patient-reported outcome assessments are described in Appendix 10.7. The primary and secondary efficacy endpoints are described in the following subsections.

The self-reported questionnaires will be administered in countries where the questionnaires have been translated into the native language of the region and linguistically validated. Any outcome measures that are participants' self-assessments should be completed before any clinical examinations are performed.

All patient-reported and clinician-reported efficacy assessments will be captured on an electronic tablet collected at site visits.

8.1.1. Primary Efficacy Outcome Measure: SLEDAI-4

The primary efficacy endpoint is the proportion of participants who achieve a SLEDAI-4 response at Week 24. A SLEDAI-4 response is defined as a ≥ 4 -point reduction in Systemic Lupus Erythematosus Disease Activity Index 2000 (SLEDAI-2K) score from baseline. To be considered a SLEDAI-4 responder, participants must complete the 24-week treatment period and comply with concomitant medication rules (Section 9.4.1). Section 4.2 provides the rationale for the selection of SLEDAI-4 as the primary efficacy measure.

8.1.2. Secondary Efficacy Outcome Measures

8.1.2.1. British Isles Lupus Assessment Group (BILAG)-based Composite Lupus Assessment (BICLA)

The BILAG-based Composite Lupus Assessment (BICLA) is a composite index used to assess disease activity in SLE. A BICLA response is defined as follows:

- Reduction of all baseline BILAG-2004 A to B or C or D; and baseline BILAG-2004 B to C or D; and no BILAG-2004 worsening in other organ systems, as defined by ≥ 1 new BILAG-2004 A or ≥ 2 new BILAG-2004 B
- No worsening from baseline in SLEDAI-2K, where worsening is defined as any increase from baseline in SLEDAI-2K
- No worsening from baseline in participants' lupus disease activity, where worsening is defined by an increase ≥ 0.30 points on a 3-point PGA visual analogue scale (VAS)
- No permanent discontinuation of investigational product, and
- No use of restricted medications beyond the protocol-allowed threshold before assessment.

8.1.2.2. Systemic Lupus Erythematosus Responder Index-4 (SRI-4)

The SRI-4 is a composite index used to assess disease activity in SLE. The SLEDAI-2K component is used to capture clinically meaningful improvement in disease activity, while the BILAG and PGA of Disease Activity components ensure that the improvement in overall disease is not accompanied by disease worsening in other organ systems. A SRI-4 response is defined as follows:

- Reduction of ≥ 4 points from baseline in SLEDAI-2K score
- No new BILAG-2004 A or no more than 1 new BILAG -2004 B disease activity score, and
- No worsening (defined as an increase of ≥ 0.3 points [10 mm] from baseline) in PGA of Disease Activity.

Participants must complete 24 weeks of the study and comply with concomitant medication rules to be considered a responder for the SRI-4 analysis (Section 9.4.1).

8.1.2.3. Lupus Low Disease Activity State (LLDAS)

An LLDAS response is defined as a low level of disease activity attained with or without use of low-dose steroids and/or tolerated standard maintenance doses of standard-of-care immunosuppressant medications (Franklyn et al. 2016).

